6.6. ECHO, ECG and Vital Sign Data Analysis

The analysis of Echocardiogram (Echo) will be based on the Safety Analysis Set. A clinically significant asymptomatic cardiac event or the LVEF abnormality is defined as an absolute decline in LVEF from baseline of more than 15 points and to a value that is below the institution's lower limit of normal. Descriptive statistics (n, mean, median, standard deviation, minimum, and maximum) will be used to summarize the LVEF change from baseline. Shift tables will also be provided for LVEF abnormality at baseline vs. on treatment (yes, no, not done: (n, %)).

The analysis of ECG results will be based on patients in the Safety Analysis Set with baseline and on-treatment ECG data, and will follow the ICH E14 guidance on the clinical evaluation of QT/QTc interval prolongation and proarrhythmic potential for non-antiarrhythmic drugs.⁹

ECG measurements (an average of the triplicate measurements) will be used for the statistical analysis and all data presentations. Any data obtained from ECGs repeated for safety reasons after the nominal time-points will not be averaged along with the preceding triplicates.

Interval measurements from repeated ECGs will be included in the outlier analysis as individual values obtained at unscheduled time points.

QT intervals will be corrected for HR (QTc) using standard correction factors [ie, Fridericia's (default correction), Bazett's, and possibly a study specific factor, as appropriate]. QTcF interval will be calculated using the Fridericia formula, as follows:

$$QTcF = \frac{QT}{\sqrt[3]{RR}}$$

Data will be summarized and listed for QT, HR, response rate (RR), PR, QRS, QTcF (and/or QTcB if deemed appropriate by overall, and by dose group. Individual QT (all evaluated corrections) intervals will be listed by study arm time and dose. The most appropriate correction factor will be selected and used for the following analyses of central tendency and outliers and used for the study conclusions. Descriptive statistics (n, mean, median, standard deviation, minimum, and maximum) will be used to summarize the absolute corrected QT interval and changes from baseline in corrected QT after treatment by study arm dose and time point. For each patient and by treatment, the maximum change from baseline will be calculated as well as the maximum post-baseline interval across time points. Categorical analysis will be conducted for the maximum change from baseline in corrected QT and the maximum post- baseline QT interval.

Shift tables will be provided for baseline vs worst on treatment corrected QT (one or more correction methods will be used) using maximum CTCAE version 4.03 Grade. Shift tables will also be provided for ECG abnormality at baseline vs. on treatment (yes, no, not done: (n, %)).

Patients experiencing clinically-relevant morphological ECG changes will be summarized (including frequency and percentage).

The effect of drug concentrations on corrected QT change from baseline may be explored graphically. Additional concentration-corrected QT analyses may be performed. Data may be pooled with other study results and/or explored further with PK/PD models.

Changes from baseline for the ECG parameters QT interval, heart rate (HR), QTc interval, PR interval and QRS interval will be summarized by treatment and visit. Categorical data analysis will follow [Section 9.3](#).

If more than one ECG is collected at a nominal time post dose (for example, triplicate ECGs), the mean of the replicate measurements will be used to represent a single observation at that time point. If any of the three individual ECG tracings has a QTc value ≥ 500 msec, but the mean of the triplicates is not ≥ 500 msec, the data from the subject's individual tracing will be described in a safety section of the study report in order to place the ≥ 500 msec value in appropriate clinical context. However, values from individual tracings within triplicate measurements that are ≥ 500 msec will not be included in the categorical analysis unless the average from the triplicate measurements is also ≥ 500 msec. Changes from baseline will be defined as the change between QTc post dose from the time-matched average of the pre-dose triplicate values on Day 1.

In addition, an attempt will be made to explore and characterize the relationship between plasma concentration and QT interval length using a PK/PD modeling approach. If a PK/PD relationship is found, the impact of subject factors (covariates) on the relationship will be examined.

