1.5.2. Rationale for Safety Monitoring Plan

1.5.2.1. Cardiac Disorders

Valvulopathy – Inhibition of the TGFβ pathways was associated in galunasertib nonclinical studies with a number of cardiac toxicities that were characterized by aneurysms and valvulopathy with associated degenerative and inflammatory changes.⁵⁰ CCl

In addition, only patients with stable cardiac disease will be enrolled and monitored with periodic assessments of vital signs, electrocardiograms (ECGs), cardiac biomarkers (troponin, high-sensitivity C-reactive protein [hs-CRP], brain natriuretic peptide [BNP]), and Doppler echocardiography. Patients with any Grade 3 treatment-related cardiac event will be discontinued from the trial.

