- 15. Anticoagulation therapy with heparin, low molecular weight heparin, vitamin K antagonists, anti-platelet agents, or factor Xa inhibitors throughout the study and for at least 28 days post the last dose of study treatment. (If anticoagulation therapy is medically indicated on trial, patients should stop treatment with PF-06952229. For those requiring temporary anticoagulant therapy, resumption of PF-06952229 treatment may be permitted after discussion with the Sponsor. In any other case, study treatment should be permanently discontinued, and the patient should enter the follow-up portion of the trial.)
- 16. Moderate or severe heart valve function defect including moderate or severe valve stenosis or regurgitation.
- 17. Evidence or history of septal aneurysm, other heart aneurysm, or any aneurysm of the major vessels.
- 18. Grade \geq 3 cardiac troponin I at baseline.
- 19. Left ventricular ejection fraction (LVEF) of ≤50% or significant valvular regurgitation.
- 20. Hypertension that cannot be controlled by medications (>150/90 mmHg despite optimal medical therapy) or requiring more than 2 medications for adequate control.
- 21. Clinically significant non-healing or healing wounds.
- 22. For patients entering the combination with enzalutamide arm, history of seizures other than isolated febrile seizure in childhood.
- 23. Has a history of a cerebrovascular accident or transient ischemic attack less than 6 months ago.
- 24. Known or suspected hypersensitivity to active ingredient/excipients of PF-06952229 or enzalutamide.

- 25. Other acute or chronic medical or psychiatric condition, including recent (within the past year) or active suicidal ideation or behavior or laboratory abnormality that may increase the risk associated with study participation or investigational product administration or may interfere with the interpretation of study results and, in the judgment of the investigator, would make the patient inappropriate for entry into this study.
- 26. Investigator site staff members directly involved in the conduct of the study and their family members, site staff members otherwise supervised by the investigator, or patients who are Pfizer employees, including their family members, directly involved in the conduct of the study.

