7.2. Echocardiogram

Echocardiogram (Echo) will be evaluated in all patients. The following parameters will be evaluated: ventricular function (including left ventricular ejection fraction [LVEF], end systolic volume [ESV] and end diastolic volume [EDV]), qualitative evaluation of chamber size, and wall motion. A Doppler examination will be completed and should include an assessment of mitral valve, atria, right ventricle, tricuspid valve, aortic valve, pulmonic valve, great vessels, and pericardium. Additional assessments will be per the study manual.

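### SAP 6.6 uses a change-from-baseline LVEF event as a shift-table category, so the baseline 'yes' row is empty by construction and falls to below LLN of 15 points or less are tabulated 'no'

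*SAP*

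**What the plan says.** SAP 6.6 gives the echocardiogram one paragraph, analysed on the Safety Analysis Set. It contains a definition and two outputs.

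- **Definition.** "A clinically significant asymptomatic cardiac event or the LVEF abnormality is defined as an absolute decline in LVEF from baseline of more than 15 points", with the second condition that the value falls under the institution's LLN. Both conditions must be met.
- **Output 1.** Descriptive statistics (n, mean, median, SD, minimum, maximum) that "will be used to summarize the LVEF change from baseline".
- **Output 2.** "Shift tables will also be provided for LVEF abnormality at baseline vs. on treatment", with categories yes, no and not done.

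SAP 5.3 defines baseline as the last value before study drug starts in Cycle 1. Protocol 4.2 excludes patients with "Left ventricular ejection fraction (LVEF) of ≤50% or significant valvular regurgitation", so every eligible patient enters above 50%.

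On valves, Protocol 1.5.2.1 explains the cardiac monitoring by nonclinical galunisertib findings, "a number of cardiac toxicities that were characterized by aneurysms and valvulopathy with associated degenerative and inflammatory changes". Protocol 7.2 asks for ventricular function, "qualitative evaluation of chamber size, and wall motion", and a Doppler examination that "should include an assessment of mitral valve, atria, right ventricle, tricuspid valve, aortic valve, pulmonic valve, great vessels, and pericardium". SAP 6.6 plans no output for the valve, great-vessel or pericardial part. SAP 9.3 sets categories for ECG and vital signs only, and Protocol 9.5 contains no echo analysis.

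**The concern.** A shift table needs a category that describes a state a patient can be in at both time points. The category chosen here is an event defined by change from baseline, which nobody can have had at baseline. That has two consequences.

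First, the baseline side of the table carries no information about LVEF. A patient who enters below the local LLN, which is possible where LLN is above 50, is shown as baseline 'no' like everyone else.

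Second, because the event also requires a fall of more than 15 points, a patient can go from normal to below LLN on treatment and still be tabulated 'no'. A reader of the study report who sees no/no in an LVEF abnormality table is likely to take it that LVEF stayed normal. In a trial with dedicated cardiac monitoring, that is worth getting right in the table shell.

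**Working it through.** The plan states no figure to reproduce here. The check is to apply the SAP 6.6 rule literally.

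**Rule.** Let b be baseline LVEF and x a later value, in whole points. The patient is flagged if b − x > 15 and x < LLN.

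**Step 1: at baseline.** Here x = b, so b − x = 0, which is not above 15. No baseline is ever flagged, whatever b or LLN. In a 3 × 3 table (yes, no, not done at each time) the baseline 'yes' row is 3 of 9 cells, all always 0. If baseline is not done, b is unknown and the fall cannot be computed. The event can therefore appear only in the cell baseline 'no', on treatment 'yes', and the table reduces to an on-treatment count.

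**Step 2: who is missed on treatment.** A value is below LLN but not flagged when b − 15 ≤ x < LLN. Such values exist whenever b < LLN + 15. For a patient starting at or above LLN, the number of whole-point values missed is LLN + 15 − b.

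The documents give no LLN, so 50 and 55 are assumptions.

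| Baseline b | Meets the fall criterion at (b − 16) or lower | Missed below LLN, if LLN = 50 | Missed below LLN, if LLN = 55 |
|---|---|---|---|
| 51 | 35 | 36–49 (14 values) | already below LLN at entry |
| 55 | 39 | 40–49 (10) | 40–54 (15) |
| 60 | 44 | 45–49 (5) | 45–54 (10) |
| 65 | 49 | none | 50–54 (5) |
| 70 | 54 | none | none |

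For example, with LLN 50 a fall from 60 to 45 is 15 points and is tabulated 'no'; a fall to 44 is 16 points and is tabulated 'yes'.

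**Step 3: does the other output fill the gap?** Summary statistics of change show how large the falls were, not where they ended. A fall from 70 to 60 and a fall from 55 to 45 are both 10 points. With LLN 50 the second crosses LLN and the first does not, and the two contribute the same number to the summary.

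**Step 4: after the fix.** If the category is LVEF below LLN at each time point, every value in the 'missed' columns is counted as below. Baseline 'below' becomes possible where LLN is above 50: at LLN 55, eligible patients entering at 51 to 54. Where LLN is 50 or lower that row stays empty for eligible patients, because Protocol 4.2 excludes LVEF of 50% or less.

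**The case against.** The strongest reply is that the SAP is defining a clinically significant event and is entitled to require both size and level. That stands. Nothing in the documents contradicts the 15-point cut-off, and it should be kept. The problem is using it as a shift category.

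A reader might infer that the table cannot show any shift. It can: the no-to-yes cell is the one of interest, and no patient who meets the definition is lost. Nor is the yes/no/not done layout out of place, since the same section plans an ECG abnormality table in that form; an ECG abnormality, however, can exist at baseline.

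A reader might also infer that valve toxicity would go unreported. The documents do not support that. Protocol 8.2.2 makes an abnormal finding an AE if it needs further testing or if the investigator or sponsor judges it one. Protocol 5.4.4 stops treatment for medically significant cardiac toxicity. Protocol 9.7 has a safety review team looking at individual data during the study. Protocol 4.2 keeps out moderate or severe valve defects and aneurysms. The signal comes from galunisertib animal studies, part of the text around it is redacted, and Protocol 1.5 reports no cardiac events in the clinical studies of that drug. What has no planned output is valve change below AE level, and whether valve grades are in the database depends on a study manual that is not available. The SAP also promises to follow the sponsor's safety reporting standard (6.2.2), which may bring an echo listing but specifies none.

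The same AE route could capture some of the smaller LVEF falls. It would not put them in the LVEF table.

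**Conclusion.** The point holds and is minor. By the SAP's own definition, the baseline 'yes' row is empty by construction, and patients who fall to below LLN by 15 points or less are tabulated 'no', with no other planned echo output showing the crossing. How many patients this affects depends on the local LLN and on entry LVEF, neither of which the documents give. Under an assumed LLN of 50 the gap closes at a baseline of 65; under 55 it closes at 70.

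The effect is on descriptive cardiac safety reporting only. The SAP has no hypotheses, and the DLT, MTD and cardiac DLT-cap rules do not use this table, so it would be wrong to read the point as a threat to dose finding or to error rates. The missing valve output supports an optional listing and nothing stronger. These statements rest on the visible text: parts of SAP section 6 are redacted, although the echo section is not.

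**What to change.** In SAP 6.6:

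1. Base the LVEF shift table on LVEF relative to the institutional LLN (at or above, below, not done), baseline against worst on treatment, by dose. The section already uses that comparison for QTc: "Shift tables will be provided for baseline vs worst on treatment corrected QT". Accept that the baseline 'below' row may be empty at sites with LLN of 50% or lower; every fall to below LLN is then still counted.
2. Keep the more-than-15-point fall to below LLN as the clinically significant event, reported as a post-baseline incidence by dose among patients with a baseline and at least one post-baseline echo.
3. Optional: list new or worsened valve, great-vessel or pericardial echo findings.

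The cost is SAP wording, one revised table shell, one incidence table and possibly one listing, all from echoes already being done. No visit, procedure or patient is added. The listing can be only as detailed as the data captured, and most entries are likely to be low-grade findings.

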7. INTERIM ANALYSES

There is no formal interim analysis planned in this study.

A final analysis will be performed when all the patients are enrolled and have completed their scheduled tumor assessments.

This is an open label study. The Pfizer study team will review safety, immunogenicity, **CCI** [REDACTED] and other data throughout the study.

9. APPENDICES

9.1. Details of Definitions of Endpoints

DLT Definition

Severity of adverse events (AEs) will be graded according to CTCAE version 5.0. For the purposes of dose escalation, any of the following AEs occurring in the first cycle of treatment (within 28 days of first dose or until the patient completes the first cycle of therapy if there are treatment delays) which are clinically significant will be classified as DLTs, unless there is a clear alternative explanation and agreed upon by investigator and sponsor (eg, clearly and incontrovertibly due to underlying disease/progression or extraneous cause) where there has been a clinically significant change from baseline:

- Clinically important or persistent toxicities that are not included in the criteria below may be considered a DLT following review by Pfizer and the Investigators. All DLTs need to represent a clinically significant shift from baseline.

Note: Labs must be repeated for confirmation. Only the lab result requiring confirmation must be repeated, not the entire panel.

Hematologic:

Any treatment-related hematologic laboratory abnormality specifically defined as:

- Thrombocytopenia Grade 4 for ≥ 7 days, or Grade 3 or 4 associated with \geq Grade 2 clinically significant bleeding or requiring platelet transfusion (for bleeding events with no grading available clinically significant bleeding is defined as required hospitalization or urgent medical intervention);
- Neutropenia Grade 4 for ≥ 7 days; Grade ≥ 3 neutropenia with infection;
- Anemia Grade 4, or Grade 3 or 4 requiring blood transfusion.

Nonhematologic:

- Grade ≥ 3 toxicities that are considered clinically significant;
- Alanine aminotransferase (ALT)/aspartate aminotransferase (AST) $>3x$ the upper limit of normal (ULN) with bilirubin $>2x$ the ULN without another explanation (eg, cholestasis) will be considered a DLT, ie, confirmed drug induced liver injury (DILI) meeting Hy's law criteria;
- Grade 3 nausea, vomiting or diarrhea that does not resolve within 4 days despite maximal supportive therapy.

Nonhematologic and Non-Hepatic:

- Any toxicity causing greater than 2 weeks of dose delay is a DLT. Note: Patients deriving clinical benefit from study treatment who experience a DLT may continue on study at a reduced dose following recovery of the AE to Grade 0-1 or baseline, only after discussion between the investigator and sponsor;
- Any toxicity preventing patients from receiving 75% of study drug during the DLT evaluation period is a DLT.

The following AEs will not be adjudicated as DLTs:

- Any Grade 3 endocrinopathy that is adequately controlled by hormonal replacement;
- Grade 3 AE of tumor flare (defined as local pain, irritation, or rash localized at sites of known or suspected tumor);
- Any Grade 5 event clearly due to underlying disease or extraneous causes;
- Isolated Grade 3 laboratory abnormalities that are not associated with clinical sequelae and are corrected with supplementation/appropriate management within 72 hours of their onset at data cut off will not be taken into account for MTD determination including but not limited to:
 - Grade ≥ 3 electrolyte abnormality lasting <72 hours, is not clinically complicated, and resolves spontaneously or responds to conventional medical interventions;
 - Grade ≥ 3 amylase or lipase that is not associated with symptoms or clinical manifestations or pancreatitis.
- A patient is classified as DLT-evaluable if he/she experiences a DLT or if he/she otherwise in the absence of a DLT receives at least 75% of the planned doses of each investigational product and has received all scheduled safety assessments during the DLT window. If a patient fails to meet these criteria, he/she may be replaced.

MTD Definition

A DLT rate of 27.5% with an equivalence interval of (22.5%, 32.5%) (note: provided the DLT rate for cardiac toxicity does not exceed 10%) will be utilized to estimate the MTD; patients will be enrolled in dose cohorts of 2-4 patients, and each patient will receive 2 courses of PF-06952229 (7 days on, 7 days off) in a 28 day cycle. Due to the discreteness of the dose levels and in the interest of the safety of patients, the estimated MTD is the highest tested dose level with DLT rate \leq approximately 32.5%. The dose finding decision will be based on a 1-cycle (28 day) DLT observation period.

At least 6 patients have been accumulated on a dose that can be predicted to be the MTD.

Recommended Phase 2 Dose (RP2D) Definition

The RP2D is the dose chosen for further investigation based on Phase 1 study results. If the MTD proves to be clinically feasible for long-term administration in a reasonable number of patients, then this dose usually becomes the RP2D. Further experience with the MTD may result in a RP2D dose lower than the MTD.

9.2. Time to Event Data Analysis Censoring Rules

Table 1. Progression Free Survival and Duration of Response

Situation	Date of Progression/Censoring¹	Outcome
Inadequate baseline assessment	First dosing date in Cycle 1	Censored
No on-study assessments	First dosing date in Cycle 1	Censored
Alive, on treatment ² and no Progression	Date of last objective tumor assessment	Censored
Progression Documented on or between scheduled tumor assessments prior to treatment discontinuation ²	Date of first objective tumor assessment showing objective progression	Progressed (Event)
Treatment discontinuation for undocumented progression	Date of last objective tumor assessment prior to discontinuation ²	Censored
Treatment discontinuation due to toxicity or other reason	Date of last objective tumor assessment prior to discontinuation ²	Censored
Death prior to first planned tumor assessment	Date of death	Death (Event)
Death without objective progression prior to treatment discontinuation ²	Date of death	Death (Event)
Death or progression after 2 or more missed tumor assessments	Date of last objective tumor assessment prior to the event	Censored

1. For date of censorship, if a tumor assessment takes place over a number of days (eg, superficial lesions one day, scans another), the last date is used as the assessment date.

2. Or within 28 days of discontinuation of treatment.

Table 2. Time to Progression

Situation	Date of Progression/Censoring¹	Outcome
Inadequate baseline assessment	First dosing date in Cycle 1	Censored
No on-study assessments	First dosing date in Cycle 1	Censored
Alive, on treatment ² and no Progression	Date of last objective tumor assessment	Censored
Progression Documented on or between scheduled tumor assessments prior to treatment discontinuation ²	Date of first objective tumor assessment showing objective progression	Progressed (Event)
Treatment discontinuation for undocumented progression	Date of last objective tumor assessment prior to discontinuation ²	Censored

Table 2. Time to Progression

Situation	Date of Progression/Censoring¹	Outcome
Treatment discontinuation due to toxicity or other reason	Date of last objective tumor assessment prior to discontinuation ²	Censored
New anticancer treatment <28 days after discontinuation of treatment without progression	Date of last objective tumor assessment prior to new anticancer treatment	Censored
Death prior to first planned tumor assessment	Start date (C1D1)	Censored
Death without objective progression prior to treatment discontinuation ²	Date of last objective tumor assessment prior to death	Censored
Progression after 2 or more missed tumor assessments	Date of last objective tumor assessment prior to the event	Censored

1. For censoring date, if a tumor assessment takes place over a number of days (eg, superficial lesions one day, scans another), the last date is used as the assessment date.

2. Or within 28 days of discontinuation of treatment.

Censoring rules for DOR will be the same as for PFS.

